3.3 VITAL SIGNS

3.3.1 *Available data*

The following vital signs parameters are collected:

- duplicate systolic (SBP) and diastolic blood pressure (DBP) in supine position.
- pulse rate.
- respiratory rate.
- body temperature.
- oxygen saturation.

Vital signs (blood pressure, pulse rate, respiratory rate, body temperature): systolic and diastolic blood pressure will be evaluated in duplicate after 5 minutes in supine position. Vital signs will be measured at the following timepoints: screening, pre-dose, every 15 minutes during the infusion (e.g., 15, 30, 45, 60, 75, 90, 105, etc.), at the end of the infusion and 30 min, 1, 2, 3, 4, 6, 8, and 20 hours after the end of the infusion and 5, 7, 14, 28, 56, and 84 days post-dose.

Oxygen saturation: will be measured at screening and continuous monitoring will occur from pre-dose to 10 hours post-dose at the following timepoints: pre-dose, every 15 minutes during the infusion (e.g., 15, 30, 45, 60, 75, 90, 105, etc.), at the end of the infusion and 30 min, 1, 2, 3, 4, 6, 8, hours after the end of infusion. Oxygen saturation will also be measured at 20 hours after the end of infusion, and 5, 7, 14, 28, 56 and 84 days post-dose and in case of early termination visit.

3.3.2 *Derivation rules*

Mean values of the duplicates will be calculated per time point and rounded as detailed in section 6.3.4. Records belonging to the same duplicate will be identified using variable VSREFID. All records of the duplicate will be used to calculate the mean, even if less or more than the expected two. The date and time of the first member of the duplicate will be assigned to this mean value. Throughout the analysis, including the derivation of baseline and abnormalities, the mean values will be used. Individual duplicate values will only be listed.

The following change from baseline abnormality categories will be defined:

- Changes from baseline:
 - Diastolic blood pressure
 - Decrease from baseline >10 mmHg
 - Increase from baseline >10 mmHg
 - Systolic blood pressure
 - Decrease from baseline >20 mmHg
 - Increase from baseline >20 mmHg

3.3.3 *Presentation of results*

Vital signs and oxygen saturation parameters will be summarised by means of descriptive statistics at each analysis time point by treatment. Actual values (with 2-sided 95% CI) and changes from baseline (with 2-sided 95% CI) will be tabulated.

For the blood pressure parameters, the number and percentage of subjects with abnormal changes from baseline will be presented at each post-baseline time point and at the worst-case analysis visit by treatment.

All vital signs data will be listed.

Graphs of the mean changes from baseline over time will be prepared for the vital signs and oxygen saturation parameters by treatment. In addition, individual graphs of the changes from baseline over time will be presented by treatment for the vital signs and oxygen saturation parameters.

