 - c. Dizziness (presyncope), or diaphoresis.
3. Severe (hypoxia, hypotension, or neurological compromise)
 - a. Cyanosis or hypoxemia (oxygen saturation \leq 92%)
 - b. Hypotension (systolic blood pressure $<$ 90 mmHg)
 - c. Confusion, collapse, loss of consciousness, or incontinence.

Clinical Study Code No.: CLI-10067AA1-01	Version No.: 6.0
EUDRACT No.: 2022-001079-15	Date: 06 July 2023

Characterisation of the immediate hypersensitivity reactions will be performed at the end of study after all clinical and biochemical data are available and analysed by Safety Advisory Committee.

Anaphylactic reactions, defined as IgE mediated, are not expected to occur during the first administration. However, when an anaphylactic reaction is suspected, CHF10067 should be discontinued immediately and appropriate therapy as per standard of care including epinephrine, diphenhydramine, corticosteroids, oxygen, and volume expansion should be administered.

Clinical criteria to diagnose anaphylaxis are summarised below [19]:

Anaphylaxis is highly likely when any 1 of the following 3 criteria is fulfilled:

1. Acute onset of illness (minutes to several hours) with involvement of the skin, mucosal tissue, or both (e.g., generalised urticaria, pruritis, flushing, or angioedema)

AND at least 1 of the following

- a. Respiratory compromise (e.g., Dyspnoea, wheeze-bronchospasm, stridor, chest tightness, or hypoxemia [oxygen saturation $\leq 92\%$])
- b. Hypotension (blood pressure < 90 mmHg) or associated symptoms of end-organ dysfunction (e.g., collapse, syncope, or incontinence).

2. **Two or more** of the following that occur after exposure (minutes to several hours):

- a. Involvement of the skin, mucosal tissue, or both (e.g., generalised urticaria, pruritis, flushing, or angioedema)
- b. Respiratory compromise (e.g., dyspnoea, wheeze-bronchospasm, stridor, chest tightness, or hypoxemia [oxygen saturation $\leq 92\%$])
- c. Hypotension (blood pressure < 90 mmHg) or drop in blood pressure ($> 30\%$ of subject's baseline) or associated symptoms of end-organ dysfunction (e.g., collapse, syncope, or incontinence)
- d. Persistent gastrointestinal symptoms (e.g., abdominal pain, nausea, or vomiting).

3. Reduced blood pressure after exposure to a known allergen for that subject (minutes to several hours):

- a. Systolic blood pressure of < 90 mmHg

OR

- b. Drop in systolic blood pressure $> 30\%$ decrease from that subject's baseline.

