12.3.5.6 Vital signs

At each post-dose timepoint the following statistics will be presented by dose level for systolic and diastolic blood pressure, pulse rate, respiratory rate, and body temperature:

- mean absolute value with its 95% CI
- mean change from baseline (i.e., the pre-dose assessment on Day 1) with its 95% CI.

Time profile plots, individual and by dose level, will be presented for change from baseline (i.e., the pre-dose assessment on Day 1).

In addition, the number and percentage of subjects with a change from baseline > 20 mmHg for systolic blood pressure and > 10 mmHg for diastolic blood pressure will be presented by treatment at each post-dose timepoint and at any post-dose timepoint.

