14.3.3.1	Vital Signs and Oxygen Saturation: Summary of Actual Values and Changes from Baseline (Safety Set) Descriptive statistics of vital signs and oxygen saturation actual values and changes from baseline per parameter and analysis time-point. Table sorted by analysis time-point. Each parameter will begin on a new page.	SAF	VST001
14.3.3.2	Blood Pressure: Summary of Abnormal Changes from Baseline (Safety Set) [KFR] Tabulation of the blood pressure abnormalities as defined in section 3.3.2 at each post-baseline analysis time point and at the worst-case analysis time point per parameter. Table sorted by analysis time point. Each parameter will begin on a new page. Only post-baseline analysis time points are shown.	SAF	VST004
ECG			
14.3.4.1	12-Lead ECG: Summary of Actual Values and Changes from Baseline (Safety Set) [KFR] Descriptive statistics of continuous 12-lead ECG (HR, PR, QRS, QTcF) actual values and changes from baseline per parameter and analysis time point. Table sorted by analysis time point. Each parameter will begin on a new page.	SAF	EGT002
14.3.4.2	QTcF: Abnormalities (Safety Set) Tabulation of the abnormalities as defined in section 3.4.2 at each post-dose analysis time point and at the worst-case analysis time-point. Table sorted by analysis time point. Only baseline and post-dose analysis time points are shown.	SAF	EGT007
14.3.4.3	QTcF: Abnormal Changes from Baseline (Safety Set) [KFR] Tabulation of the QTcF change abnormalities as defined in section 3.4.2 at each post-baseline analysis time point and at the worst-case analysis time point. Table sorted by analysis time point. Only post-baseline analysis time points are shown.	SAF	EGT008
LUNG FUNCTION			
14.3.5.1	Spirometry: Summary of Actual Values and Changes from Baseline (Safety Set) Descriptive statistics of spirometry parameters actual values and changes from baseline per parameter and analysis time point. Table sorted by analysis time point. Each parameter will begin on a new page.	SAF	TPT001

	Statistical Analysis Plan		
CLI-10067AA1-01	Final Analysis	Final 1.0	of 30MAY2024

Number	Title	Analysis Set	TLFs Library Template Number
14.3.5.2	Spirometry: Summary of Relative Changes from Baseline (Safety Set) [KFR] Descriptive statistics of relative changes from baseline in spirometry results per parameter and analysis time point. Table sorted by analysis time point. Only post-baseline analysis time points are shown.	SAF	TPT004

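### Key Table 14.3.3.2 classes blood pressure only by 20/10 mmHg changes, and no table counts subjects at the systolic limits that Protocol 7.2.2.5.1 uses for reactions

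*SAP*

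**What the plan says.** Protocol 12.3.5.6 bases its blood-pressure count on this limit: "change from baseline > 20 mmHg for systolic blood pressure and > 10 mmHg for diastolic blood pressure". SAP 3.3.2 carries this out and splits it by direction: "Decrease from baseline >20 mmHg" for systolic, "Decrease from baseline >10 mmHg" for diastolic, and the matching increases. Table 14.3.3.2, marked as a key first result, counts those categories for every time point after baseline and for the worst case. It has no other blood-pressure category.

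Protocol 7.2.2.5.1 uses two further systolic limits. In the reaction grading, the severe grade includes "Hypotension (systolic blood pressure $<$ 90 mmHg". In the anaphylaxis criteria, the third criterion lists systolic below 90 mmHg or "Drop in systolic blood pressure $> 30\%$ decrease from that subject's baseline"; similar blood-pressure limits appear in the second criterion. The SAP uses neither limit.

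Actual systolic values are summarised in Table 14.3.3.1, including the minimum (SAP 6.4.1). Under SAP 6.2.4, tables and figures take the reading closest to target in each window, and other readings are only listed. The worst-case visit of SAP 6.2.5 does include unscheduled readings, but it serves only the abnormalities that the SAP has defined.

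**The concern.** Safety is the primary objective. The protocol treats immediate hypersensitivity reactions as an anticipated effect of the drug class and has blood pressure read every 15 minutes during the infusion and often afterwards. One would expect the key blood-pressure table to count the limits that the protocol itself attaches to such reactions. It does not. A value below the protocol's limit can be classed as not abnormal, and a large relative fall is counted together with a modest one. QTcF, by contrast, has both actual-value and change categories in SAP 3.4.2.

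At stake is how readily a reader of the key table can see whether any subject reached those limits, with 6 subjects per active arm and 6 pooled placebo subjects.

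**Working it through.** The plan gives no rate or power figure on this point, so there is none to reproduce. The check has three parts.

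**1. Which protocol-limit values escape the systolic flag?** Let b be the baseline and x a later systolic value. The SAP flags a decrease when b − x > 20.

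- Limit x < 90: it escapes when b − x ≤ 20, so b ≤ x + 20 < 110. Whole-number baselines from 90 to 109 mmHg are exposed. From 110 upward, any value below 90 is flagged.
- Limit of a fall above 30%: the fall exceeds 0.30 × b, which is at least 20 mmHg once b ≥ 20 / 0.30 = 66.7. In practice every such fall is flagged.

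| Baseline to value (mmHg) | Fall | Protocol limit reached | SAP systolic flag |
|---|---|---|---|
| 108 to 88 | 20 (18.5%) | below 90 | no |
| 100 to 85 | 15 (15.0%) | below 90 | no |
| 110 to 89 | 21 (19.1%) | below 90 | yes |
| 150 to 129 | 21 (14.0%) | none | yes |
| 150 to 104 | 46 (30.7%) | fall above 30% | yes, same cell as the row above |

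No eligibility criterion in Protocol 4.2 or 4.3 sets a minimum blood pressure, so baselines of 90-109 mmHg can be enrolled.

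**2. How often would the existing flag arise by chance?** The documents give no within-subject SD (s), so it is assumed. The other assumptions are no drug effect, normal independent readings, and a baseline measured with the same error. SAP 6.2.4 has 22 infusion windows and 9 post-infusion windows; with 6 later visit days that makes 37 time points. The infusion time is redacted; a 1-hour infusion (assumed) gives 4 + 9 + 6 = 19.

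- At one time point, P(fall > 20) = Φ(−20 / (s√2)). At s = 5 this is 0.2%, at s = 7 it is 2.2%, and at s = 9 it is 5.8%. Of 6 subjects, the last two are 6 × 0.022 = 0.13 and 6 × 0.058 = 0.35.
- At any of 19 to 37 time points (simulation): 3-5% at s = 5, 28-37% at s = 8, and 18-46% across s = 7 to 9. Of 18 active subjects at 37 time points, that is 0.8 at s = 5 and 6.6 at s = 8.

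Positive correlation between readings would lower the any-time-point figures.

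**3. How would the two protocol limits behave as counts?** Same model, any of 37 time points:

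| True mean systolic (mmHg) | s | Below 90 | Fall above 30% |
|---|---|---|---|
| 125 | 8 | 0.02% | 0.2% |
| 125 | 10 | 0.9% | 3.1% |
| 110 | 8 | 21% | 1.1% |
| 110 | 10 | 57% | 8.5% |

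Now assume true means with average 130 and SD 15, and 23 readings. Among subjects whose measured baseline is below 110, 33-43% go below 90 at least once by chance at s = 7 to 9. The limit of 90 is therefore specific at ordinary baselines and non-specific at low ones.

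**The case against.** The case for leaving the table alone is substantial.

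- The 20/10 categories come from Protocol 12.3.5.6. A reader might infer that the SAP departs from the protocol; it does not. The omission is common to both documents.
- A reader might infer that reaction-level hypotension disappears from the report or survives only in a listing. The documents do not support that. Table 14.3.3.1 prints the minimum systolic value per arm and window, Figure 16.2.9.1 plots each subject's changes, and Listing 16.2.9.1 holds every value. Hypersensitivity reactions have their own eCRF page with severity, a count in Table 14.3.1.1 (also a key first result) and Listing 16.2.7.10. Clinically significant findings must also be reported as adverse events.
- A reader might infer that both protocol limits can be missed at low baselines. Only the limit of 90 can, and such a subject may still be flagged on diastolic pressure.
- Confusion with chance fluctuation applies mainly to the any-time-point row. Rows by time point are much cleaner, and decreases are counted apart from increases.
- The protocol limits are diagnostic and grading features, used together with other signs or a known allergen. Counting them does not count reactions. Nor could any count table show whether the drug causes hypotension with 6 subjects per active arm and no power calculation.

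All of this stands, and it keeps the point small. It does not close the gap. The minimum in Table 14.3.3.1 uses only the reading closest to target, so a lower off-target reading during a reaction is only listed. The figure shows changes, not actual pressures, under the same selection rule. The reaction count is not split by severity or by hypotension, and it depends on the investigator recognising a reaction. The one row that takes in unscheduled readings classifies them by 20/10 alone.

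**Conclusion.** The point holds as an optional, cheap improvement. No planned table counts subjects with systolic pressure below 90 mmHg or a fall above 30%. For baselines of 90 to 109 mmHg the first can occur with no systolic flag; the second is flagged but not told apart from a fall just over 20 mmHg. These statements are arithmetic and rest on no assumption.

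The extent of dilution does rest on an assumption: about 3-5% of subjects flagged by chance at any time point at a within-subject SD of 5 mmHg, and 18-46% at 7-9 mmHg, with independent readings. The documents give neither the SD nor the correlation, so no single figure should be quoted. The weakness lies in one summary table; the underlying data remain available elsewhere in the report.

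**What to change.** Keep the existing categories. Add to SAP 3.3.2 and Table 14.3.3.2 the number and percentage of subjects with (a) systolic pressure below 90 mmHg and (b) a systolic fall of more than 30% from baseline. Show both at each time point, and once for any reading, scheduled or unscheduled, during the infusion or within 24 hours of it, which is the reaction window in Protocol 7.2.2.5.1. State whether the 24 hours run from the start or the end of the infusion. Give the baseline value for each subject counted, because a value below 90 alone says little when baseline is low.

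This is a descriptive tabulation of limits already in the protocol; it sets no clinical rule and changes no management. The cost is a few lines of SAP text, two added categories and some programming on data already collected. Record it in SAP 7.1 if the blind is unbroken; otherwise label it as added after unblinding.

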4.2 Inclusion Criteria

Subjects must meet all the following inclusion criteria to be eligible for enrolment into the study:

1. Subject's written informed consent obtained prior to any study-related procedure.
2. Males or females, of any race, aged ≥ 40 years of age.
3. Body mass index (BMI) between 18.0 and 35.0 kg/m^2 , inclusive.
4. Body weight ≥ 45 kg.

Clinical Study Code No.: CLI-10067AA1-01	Version No.: 6.0
EUDRACT No.: 2022-001079-15	Date: 06 July 2023

5. Diagnosis of IPF as defined by current ATS/ERS/JRS/ALAT guidelines (2022) which will include patients with an usual interstitial pneumonia (UIP) pattern or probable UIP pattern with confirmation of IPF diagnosis based on the Multi-Disciplinary Team Discussion (excluding other possible etiological causes of the high-resolution computed tomography [HRCT] pattern). Where a lung biopsy is available, the computerized tomography (CT) pattern and biopsy results must be compatible with a diagnosis of IPF.^[1]

Diagnosis of IPF must be within the past 5 years prior to enrolment, and in the opinion of the Investigator, has been stable for at least 3 months.

6. Subjects not receiving any IPF treatment (including subjects with previous use of antifibrotic treatment that has been stopped for at least 2 weeks prior to screening) or receiving well-tolerated standard of care approved treatments at a stable dose for at least 8 weeks prior to screening (nintedanib or pirfenidone) and it is anticipated the dose will remain unchanged throughout the study.
7. Oxygen saturation $\geq 92\%$ at rest by pulse oximetry while breathing ambient air at screening **and prior to randomization**.
8. Forced vital capacity (FVC) $\geq 50\%$ of predicted and ratio of forced expiratory volume in the first second (FEV₁)/FVC ≥ 0.7 at screening.
9. Diffusing capacity of the lung for carbon monoxide (D_{LCO}; corrected for haemoglobin) $\geq 35\%$ at screening.
10. Able to understand the study procedures and the risks involved.
11. Female subjects:
 - a. Women of childbearing potential (WOCBP) fulfilling 1 of the following criteria:
 - i. WOCBP with fertile male partners: they and/or their partner must be willing to use a highly effective birth control method preferably with low user dependency from the signature of the informed consent and until the last study visit or
 - ii. WOCBP with non-fertile male partners: contraception is not required in this case.
12. Males fulfilling one of the following criteria:

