7.2.7.3 Oxygen saturation

Oxygen saturation will be measured by continuous pulse oximetry at screening and from pre-dose to 10 hours post-dose at the following timepoints: pre-dose, every 15 minutes during the infusion (e.g., 15, 30, 45, 60, 75, 90, 105, etc.), at the end of infusion and 30 min, 1, 2, 3, 4, 6, 8 hours after the end of the infusion. Oxygen saturation will also be measured at 20 hours after the end of the infusion, and 5, 7, 14, 28, 56, and 84 days post-dose and in case of early termination visit.

For inclusion criterion no.7, if the criterion is not met at screening or at the Day 1 visit, the subject will repeat the test. If at that time the values fall within the ranges specified, the subject can be included in the study, otherwise the subject will be discharged and recorded as screening failure.

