12.3.5.4.3 Oxygen saturation

The oxygen saturation will be summarised by dose level as absolute value and change from baseline (i.e., the pre-dose assessment on Day 1) at each post-dose timepoint using descriptive

Clinical Study Code No.: CLI-10067AA1-01	Version No.: 6.0
EUDRACT No.: 2022-001079-15	Date: 06 July 2023

statistics and 95% CIs. Time profile plots by dose level will be presented for mean changes from baseline.

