6.2.2 Baseline and change from baseline

The baseline value is the last non-missing value, including unscheduled assessments, before the administration of the study treatment. In case this results in more than one record with the same date and time, the unscheduled record is selected as baseline.

Note: decisions on whether a different baseline should be used in the analysis will be fully documented in the DRR.

Change from baseline is defined as:

Change from baseline at time point t = value at time point t – baseline value.

Relative change from baseline at time point t is defined as follows:

- When baseline value is not zero: $100*((\text{value at time point t} - \text{baseline value}) / \text{baseline value})$
- When both baseline value and value at time point t are zero: not calculated
- When baseline value is zero and value at time point t is not zero: not calculated

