Per parameter and analysis window, the value closest to the target time will be used in analysis tables and figures, other values will only be listed. If more than one value is located at the same distance from the target, then the latest in time will be selected. The value latest in time will be identified using, in order of preference, the assessment time, the visit and time point label or the group identifier. Missing values are removed before the selection is made.

Partially missing assessment dates or times disabling allocation to analysis windows will not be imputed and thus these assessments will not be considered in the per-time point analysis, except for the derivation of the worst.

6.2.5 *Worst-case*

A worst-case analysis visit (presented in the analysis as ‘At Any Time Point’, or similar) will be created for parameters for which abnormalities are defined to summarise values considered as the worst-case.

The worst-case analysis visit will be derived within the treatment phase, including scheduled and unscheduled assessments as well as the early termination visit assessments. Only post-baseline assessments will be considered for the worst-case analysis visit.

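### Oxygen saturation has no worst-case row and no rule for readings taken on oxygen, so a fall away from the selected reading can be missed in the summary tables and plots

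*SAP*

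**What the plan says.** **Before dosing.** Inclusion criterion 7 (protocol 4.2) sets the eligibility reading "at rest by pulse oximetry while breathing ambient air at screening" and repeats the check before randomisation. Protocol 12.3.5.4.3 takes change from the Day 1 pre-dose assessment. SAP 6.2.2 states: "The baseline value is the last non-missing value, including unscheduled assessments, before the administration of the study treatment". It does not mention a breathing condition.

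**After dosing.** Protocol 7.2.7.3 states: "Oxygen saturation will be measured by continuous pulse oximetry at screening and from pre-dose to 10 hours post-dose at the following timepoints". The schedule follows. Neither that section, the schedule footnotes nor SAP 3.3 says whether post-dose readings are on ambient air, or whether oxygen use is recorded with them.

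**Analysis.** SAP 3.3.3 states: "Vital signs and oxygen saturation parameters will be summarised by means of descriptive statistics at each analysis time point by treatment". Under SAP 6.2.4, within each window, "the value closest to the target time will be used in analysis tables and figures, other values will only be listed". Under SAP 6.2.5 a worst-case visit "will be created for parameters for which abnormalities are defined". SAP 3.3.2 defines such categories for systolic and diastolic blood pressure only. QTcF (SAP 3.4.2) and laboratory values (SAP 3.2.2) have their own; saturation has none.

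**Oxygen as treatment.** For suspected anaphylaxis, protocol 7.2.2.5.1 foresees "appropriate therapy as per standard of care including epinephrine, diphenhydramine, corticosteroids, oxygen, and volume expansion".

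**The concern.** Saturation is a named safety variable (protocol 9.1) under the primary objective, in a population with lung disease. Oxygen is given to subjects whose saturation falls, so mixing readings on air and on oxygen errs in one direction: it makes the post-dose values look better. Keeping the closest-to-target reading adds a second route, because a fall that recovers between targets is displaced even if no oxygen is given. Blood pressure, QTcF and laboratory values each have an any-time-point summary that would catch such an excursion; saturation does not. A reader of the saturation means and plots could then take them as more reassuring than the recorded data justify.

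**Working it through.** The documents give no saturation effect, variance or power figure, so there is no planned figure to reproduce. The check traces one low reading through the rules and then sizes the effect with assumed values.

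**1. Tracing the reading**

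- The 45-minute window runs from minute 38 to minute 52 (SAP 6.2.4). A low reading at minute 40 is 5 minutes from target; the scheduled minute-45 reading is 0 minutes from target. The table and both figures use minute 45.
- The 8-hour window runs from 421 to 840 minutes after the end of infusion, a span of 840 - 421 = 419 minutes, and it too keeps one reading.
- The last saturation window ends at 1560 minutes (1560/60 = 26 hours) after the end of infusion. Later time points follow the eCRF visits. Unscheduled readings are then not analysed unless the data review decides otherwise.
- SAP 6.4.1 includes the minimum across subjects at each time point, but it is taken after the selection, so a displaced reading cannot appear in it.
- The individual plots use the selected readings too.
- SAP 6.2.5 would pick up unscheduled and early-termination values, but it does not apply to saturation.

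**2. Size, with assumed saturation values**

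There are 6 subjects per dose (protocol 12.1), and pooled placebo is also 3 x 2 = 6. Assume that one subject goes from 94% to 86% and that the other five do not change.

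Mean change using the low value: (86 - 94)/6 = -1.33 points; minimum change -8.

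Mean change as tabulated: (selected reading - 94)/6. The difference from -1.33 is (selected reading - 86)/6.

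| Selected on-oxygen reading | Tabulated mean change | Difference | Tabulated minimum change |
|---|---|---|---|
| 97% | 3/6 = +0.50 | 11/6 = 1.83 | 0 |
| 94% | 0/6 = 0 | 8/6 = 1.33 | 0 |
| 92% | -2/6 = -0.33 | 6/6 = 1.00 | -2 |

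In the pooled active group (n = 18) the same differences are 11/18 = 0.61, 8/18 = 0.44 and 6/18 = 0.33 points.

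**3. The same with some spread in the other subjects**

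Let five subjects change by -1, 0, 0, 0 and +1, and let the sixth go from 95% to 86% with a selected reading of 97%.

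- As tabulated: (0 + 2)/6 = +0.33 (t-based 95% CI -0.75 to 1.42), minimum -1.
- Using the low value: (0 - 9)/6 = -1.50 (95% CI -5.41 to 2.41), minimum -9.

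Over four assumed cases with lowest values of 84% to 88% and on-oxygen readings of 95% to 98%, the mean shifts by 1.3 points, (96 - 88)/6, to 2.3 points, (98 - 84)/6.

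**The case against.** The strongest reply is that the event itself would not be lost. Protocol 7.2.2.5.1 asks for saturation to be recorded at a reaction and uses saturation in grading its severity. SAP 3.1 collects hypersensitivity reactions on a dedicated form, counts them by treatment in the adverse event overview and lists them. New clinically significant abnormalities are recorded as adverse events. The numerical escalation stopping criteria (protocol 6.2.2.1) rest on adverse events, not on mean saturation. All readings are listed. This stands, and it confines the problem to the saturation table and plots.

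Three further points also stand:

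- A reader might infer that the plan tabulates no lowest saturation at all. It does tabulate one: the minimum across subjects at each time point. If the selected reading precedes oxygen, that minimum and the individual plot show the fall. What is missing is each subject's lowest value over time.
- A reader might infer that oxygen use is expected to be common. The documents do not support that. Oxygen is named only for suspected anaphylaxis, and the protocol does not expect IgE-mediated reactions at a first dose. The allowance for treating exacerbations (protocol 5.2) does not mention oxygen.
- A reader might infer that the mean change will reverse sign. It does so only if the selected on-oxygen reading exceeds baseline, as the 92% and 94% rows show.

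None of this supplies the missing subject-level summary. A count of reactions does not show how far saturation fell, and nothing in the plan marks a listed value as taken on oxygen.

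**Conclusion.** The gap is real and modest. As planned, a desaturation that is off target, or treated before the selected reading, can show as no change or a rise in Table 14.3.3.1 and its figures, with the low value only in the listing. One such subject moves a six-subject mean by 1.00 to 1.83 points in the main illustration.

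This rests on three assumptions: the saturation values are illustrative; the pre-dose baseline is on ambient air by inference from inclusion criterion 7, since no baseline rule says so; and the low reading is recorded. The documents do not say how often oxygen would be used, or whether the eCRF already captures it. They do not support a claim that harm would be hidden from the report as a whole, because reactions and adverse events are counted by treatment.

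**What to change.** 1. In SAP 3.3.2 and 3.3.3, define the saturation worst case as each subject's lowest post-dose value. Add that value and its change from baseline to Table 14.3.3.1 as a worst-case row by treatment, including unscheduled and early-termination readings. This uses the mechanism already in SAP 6.2.5 and needs no cut-off.
2. Where oxygen use and its times are recorded, flag those readings in Listing 16.2.9.1 and tabulate the number of subjects on oxygen at each time point. Give a supplementary summary of change that leaves flagged readings out, with the planned summary unchanged beside it.
3. Do not carry the last ambient-air value forward into later windows. That would be an imputation, contrary to the observed-cases rule in SAP 6.3.1, and would treat a brief low as the value at the scheduled time.

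**Cost.** Step 1 is SAP wording and one table row. Step 2 needs slightly more data review. Under SAP 5.5.1 medications can carry times but procedures carry dates only, so a per-reading flag may not be derivable if oxygen is recorded as a procedure. Patient care does not change.
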